5.2. Sample Size Determination

Assuming a 30% screen fail rate, approximately 85 participants will be screened to achieve 60 participants randomly assigned to study intervention for an estimated total of 52 evaluable participants.

The sample of 52 evaluable participants provides more than 87% power to the primary endpoint. This calculation is based on a 2-sample t-test, assuming a mean change from baseline to Week 12 in the UAS7 for LY3454738 and for placebo of 17 points and 10 points, respectively, a standard deviation of 7 points for the change from baseline, and a 0.05 two-sided significance level.

5.3. General Considerations

This plan describes *a priori* statistical analyses for efficacy, health outcomes, and safety that will be performed.

Statistical analysis of this study will be the responsibility of Eli Lilly and Company (Lilly). The statistical analyses will be performed using SAS[®] Version 9.4 or higher.

Not all displays described in this SAP will necessarily be included in the clinical study report (CSR). Not all displays will necessarily be created as a "static" display. Some may be incorporated into interactive display tools instead of or in addition to a static display. Any display described in this SAP and not included in the CSR would be available upon request.

For continuous measures, summary statistics will include sample size, mean, standard deviation (SD), minimum, median, and maximum. The 1st quartile and 3rd quartile may also be presented. For categorical measures, summary statistics will include the sample size, frequency count, and percentage. Percentages will be presented to 1 decimal place unless otherwise stated. Percentages will not be presented for zero counts. Incidence rates and 95% confidence interval (CI) will be displayed for select safety endpoints.

Statistical tests of treatment effects and CIs will be performed at a 2-sided significance level of 0.05, unless otherwise stated.

All p-values will be rounded up to 3 decimal places. For example, any p-value strictly greater than 0.049 and less than or equal to 0.05 will be displayed as 0.050. This guarantees that on any printed statistical output, the unrounded p-value will always be less than or equal to the displayed p-value. A displayed p-value of 0.001 will always be understood to mean ≤ 0.001 . Likewise, any p-value displayed as 1.000 will be understood to mean ≥ 0.999 and ≤ 1 .

5.3.1. Analysis Populations

Entered: All participants who sign the informed consent form.

Modified Intent-to-Treat (mITT): All participants randomly assigned to study intervention and who take at least 1 dose of study intervention. Participants will be analyzed according to the intervention to which they were assigned.

Per-Protocol (PPS) population: The PPS populations is defined as all randomized patients who do not commit an Important Protocol Deviation (IPD) that could potentially compromise efficacy results. For more details, patients who missed more than one dose in Period 2 or were enrolled inadvertently will be excluded from Per-Protocol-Set.

Safety: All participants randomly assigned to study intervention and who take at least 1 dose of study intervention. Participants will be analyzed according to the intervention they actually received within each study period.

Pharmacokinetic (PK) Analysis: All participants randomly assigned to study intervention and who take at least 1 dose of study intervention and have PK data available.

Efficacy analyses will be conducted on the Modified Intent-to-Treat (mITT) Population. This set includes all data from all randomized participants receiving at least 1 dose of the IP according to the treatment the participants were assigned.

Safety analyses will be conducted on the Safety Population. This set includes all data from all randomized participants receiving at least 1 dose of the IP according to the treatment the participants actually received.

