# 4.2. Scientific Rationale for Study Design

Patients with CSU whose symptoms are not well controlled by licensed doses of antihistamines are appropriate for a novel investigational product (IP) with immunomodulating properties. A double-blind, placebo-controlled design limits bias for both patient and investigator assessments and enables a clearer interpretation of the effects of active drug. One active dose level of

LY3454738 will allow for an evaluation of safety and efficacy and will provide information to guide dose selection in future studies.

Study treatment will be provided during two study periods (Period 2 and Period 3). Study treatment in Period 2 is designed to evaluate the primary endpoint, which is the mean change from baseline in the Urticaria Activity Score (UAS) at the Week 12 visit. The Urticaria Activity Score Over 7 Days (UAS7) assesses the burden of itch and hives in CSU. It is used widely in CSU trials and has been accepted by the FDA as a primary endpoint for trials conducted for approval of new drugs. Evaluation of the primary endpoint at the Week 12 time point is appropriate, based on previous clinical trials of systemic therapies in CSU (Maurer et al. 2013; Saini et al. 2015).

The crossover in Period 3 allows for an evaluation of safety and durability of efficacy in participants who received LY3454738 in Period 2. This study period also allows participants who were randomized to placebo in Period 2 to receive LY3454738 in Period 3 for an equal treatment duration as in Period 2.

The post-treatment follow-up in Period 4 will allow for continued safety monitoring after the last dose of LY3454738. The last dose given in Period 3 is at Week 22. This is 2 weeks before the last visit in Period 3 (Week 24, Visit 16) and a total of 12 weeks before the last post-treatment follow-up visit (Week 34, Visit 802). A follow-up period of a similar duration was used after the last dose of LY3454738 in the single- and multiple-dose cohorts in Phase 1 Study FRCC. LY3454738 is expected to be undetectable in the serum after 5 half-lives. The terminal half-life of LY3454738 is approximately 2 weeks, based on pharmacokinetic (PK) data from the Phase 1 Study FRCC. Therefore, for the present study, the planned duration of safety follow-up is adequate, as this duration covers approximately 6 half-lives.

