## 4.3. Justification for Dose

The planned dose of 500 mg IV Q2W for patients with CSU was chosen based on an analysis with preliminary human PK and receptor occupancy data from healthy subjects who received single (1 to 1000 mg) or repeat (200 mg x 2 doses) IV doses of LY3454738 in the Phase 1 Study FRCC. Based on the preliminary analysis, the half-life of LY3454738 is approximately 2 weeks, and a Q2W dose of 500 mg is expected to achieve approximately 90% saturation of the receptor at the trough drug concentration at steady state ( $C_{min,ss}$ ). Receptor occupancy is used as a surrogate of pharmacological activity, and receptor saturation is desired to maximize the probability of achieving clinical efficacy.

This 500 mg IV Q2W dose was predicted to achieve a steady-state exposure that is similar to the maximum exposure achieved after the highest dose tested as a single dose in Study FRCC (that is, 1000 mg). In the single-ascending dose portion of Study FRCC, there were no dose-limiting safety findings. See the IB for additional information.

Dose selection is further supported by preclinical toxicity data. LY3454738 was evaluated in cynomolgus monkeys over a 3-month dosing period, during which LY3454738 was administered once weekly at doses of 0, 15, or 50 mg/kg subcutaneous or 170 mg/kg IV (13 total doses). The no-observed-adverse-effect level (NOAEL) in this study was 170 mg/kg, and this provides a margin of safety of  $\geq$ 33-fold (based on mg/kg dose or estimated human exposure) to a repeated dose of 500 mg Q2W. See the IB for additional information supportive of the dose selection.

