## 6.1. Study Interventions Administered

#### Study interventions

This study involves a single dose level of LY3454738 and placebo, as shown below.

Treatment Name	LY3454738	Placebo				
Dosage Formulation	Lyophilized powder	0.9% sodium chloride				
Dosage Level	500 mg	not applicable				
Routes of Administration	IV infusion	IV infusion				
Dosing Instructions	One dose every 2 weeks	One dose every 2 weeks				

Abbreviation: IV = intravenous.

LY3454738 is supplied for clinical trial use as a lyophilized powder formulation in a glass vial. Vials will be supplied in cartons, with the appropriate quantity specific to the planned dispensing schedule of the IPs.

When the IPs are prepared for dosing according to instructions (Section 6.2) it will not be possible to distinguish LY3454738 from placebo.

All participants should be monitored for 30 minutes or longer after dosing, according to investigator practice or local standard of care. Sites must have resuscitation equipment, emergency drugs, and appropriately trained staff available during the infusion and monitoring period, or until completion of all required post-dosing activities (whichever is longer).

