5.3.2. Definition of Baseline and Postbaseline Measures

The baseline value for Period 2 is defined as the last nonmissing measurement on or before the date of first study drug administration (expected at Week 0). The baseline value for Period 3 is the last available value before the initial dose in Period 3 (expected at Week 12). Other definitions of the baseline value may be used to conduct additional supporting analyses.

A number of efficacy outcome measures are in the form of weekly scores derived from patient daily diary data. For these measures, the weekly score will be derived from the 7 days immediately prior to the study visit. The baseline score will be derived from the 7 days prior to Day 1 (Visit 2) for Period 2, and 7 days prior to Day 85 (Visit 9) for Period 3.

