5.7.2. Adverse Events

Adverse events are recorded in the eCRFs. Each AE will be coded to system organ class (SOC) and preferred term (PT) using the Medical Dictionary for Regulatory Activities (MedDRA) version that is current at the time of database lock. Severity of AEs is recorded as mild, moderate, or severe.

A TEAE is defined as an event that either first occurred or worsened in severity after the first dose of study treatment and on or prior to the last visit date during the analysis period. For each event classification term, the number of participants experiencing a TEAE with that classification term will be tabulated. For this study, the TEAEs should be counted by periods: TEAEs for Period 2 for V2-V9; TEAEs for Period 3 for V10-V16; TEAEs for Period 4 after V16.

Treatment-related TEAEs are defined as events that are indicated by the investigator on the eCRF to be related to treatment. For events that are gender specific, the denominator and computation of the percentage will include only participants from the given gender.

Adverse events are classified based upon the MedDRA PT. The MedDRA Lowest Level Term (LLT) will be used in defining which events are treatment-emergent. The maximum severity for each LLT during the baseline period up to first dose of the study medication will be used as baseline. If an event with missing severity is preexisting during the baseline period, and persists during the treatment period, then the baseline severity will be considered mild for determining TEAE (that is, the event is treatment-emergent if the severity is coded moderate or severe postbaseline and not treatment-emergent if the severity is coded mild postbaseline). If an event occurring postbaseline has a missing severity rating, then the event is considered treatment-emergent. The day and time for events where onset is on the day of the first dose of study treatment will both be used to distinguish between pretreatment and posttreatment in order to derive treatment-emergence. Should there be insufficient data for AE start date to make this comparison (for example, the AE start year is the same as the treatment start year, but the AE start month and day are missing), the AE will be considered treatment-emergent.

In an overview table, the number and percentage of subjects who experienced a TEAE or serious adverse event (SAE), died due to an AE, or discontinued from study due to an AE will be summarized by treatment.

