The frequency and percentages of patients with TEAEs will be summarized by treatment using MedDRA PT nested within SOC. Events will be ordered by decreasing frequency within SOC. The frequency and percentages of patients with TEAEs by maximum severity will also be summarized by treatment using MedDRA PT nested within SOC.

Fisher's exact test will be performed to compare percentages for each LY3454738 dose group and Placebo at both the SOC and PT levels.

Listings will be presented for all AEs, all SAEs, all AEs leading to death, all AEs leading to study drug temporary interruption, and all AEs leading to discontinuation from the study.

In this study, the following events are being captured as study endpoints and will not be reported as AEs:

- Pruritus (itching)
- Angioedema
- Hives (wheals)

Information on these events will be captured via the UPDD (patient electronic diary).

However, if any of these events is an SAE, the event should be reported as an SAE.

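### Period 3 has no valid placebo comparator for safety: the crossover has no washout and the half-life is about 2 weeks, yet the SAP does not limit its LY3454738-versus-placebo safety tests to Period 2

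*SAP*

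**What the plan says.** **Dosing through the crossover.** Protocol 6.1 gives "One dose every 2 weeks". The dosing row of the Schedule of Activities marks Weeks 0, 2, 4, 6, 8 and 10, and then Week 12, the first Period 3 infusion. Sequence Group 1 therefore has its last LY3454738 infusion at Week 10 and its first placebo infusion one ordinary dosing interval later.

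**Persistence of the drug.** Protocol 4.2 states: "The terminal half-life of LY3454738 is approximately 2 weeks, based on pharmacokinetic (PK) data from the Phase 1 Study FRCC". It adds: "LY3454738 is expected to be undetectable in the serum after 5 half-lives". Protocol 4.3 expects the chosen regimen to give "approximately 90% saturation of the receptor at the trough drug concentration at steady state".

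**Grouping for safety.** Protocol 9.3 and SAP 5.3.1 agree: "Participants will be analyzed according to the intervention they actually received within each study period". SAP 5.7 says instead that safety patients are grouped by the product randomized at Week 0.

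**Safety comparisons.** SAP 5.7.2 says: "For this study, the TEAEs should be counted by periods", with separate windows for Visits 2 to 9, Visits 10 to 16, and after Visit 16. It then says: "Fisher's exact test will be performed to compare percentages for each LY3454738 dose group and Placebo at both the SOC and PT levels". It does not name the period. SAP 5.7.2.2 repeats the Fisher test for discontinuations due to adverse events. SAP 5.7.3 plans a treatment ANCOVA for laboratory change, and SAP 5.7.4 applies the same methods to vital signs; neither is limited to Period 2. Some by-treatment displays are not split by period: SAEs and adverse-event discontinuations over the study drug period (5.7.2.1, 5.7.2.2), and creatinine shifts over Periods 2 and 3 (5.7.6.2).

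**Baseline.** SAP 5.3.2: "The baseline value for Period 3 is the last available value before the initial dose in Period 3 (expected at Week 12"). SAP 5.7.3 uses the last observation in the baseline period. Neither document has a carry-over rule for safety.

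**The concern.** A placebo column should estimate what happens without the drug. In Period 3 no participant can supply that. Those receiving placebo have just completed 12 weeks of LY3454738 and still carry it; the others are receiving it. Late or persisting effects, such as infections or low cell counts, would be counted against placebo if grouping is by treatment received. If grouping is by original randomization, events on active drug in Sequence Group 2 would be counted against placebo.

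Either way, a Period 3 contrast, or one that pools periods, may make the drug look closer to placebo than it is. This matters because Protocol 4.2 names safety after LY3454738 as a purpose of Period 3, and a small trial with a reassuring Fisher table is easily over-read.

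**Working it through.** **Inputs.** Half-life 2 weeks and the 5-half-life rule (Protocol 4.2); last active dose at Week 10 and Period 3 from Week 12 to 24 (Schedule of Activities); 60 randomized 3:1, so about 45 and 15 (SAP 4.1, 4.2).

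**The protocol's own figure.** Protocol 4.2 says 12 weeks of follow-up covers about 6 half-lives: 12 / 2 = 6. This reproduces.

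**Time with detectable drug in Period 3.**
- Clearance point: 10 + 5 × 2 = Week 20.
- Share of Period 3: (20 − 12) / (24 − 12) = 8/12 = 67%.
- In the Visit 10 to 16 adverse-event window (Weeks 13 to 24): (20 − 13) / (24 − 13) = 7/11 = 64%.
- If *approximately 2 weeks* means 1.5 to 2.5 weeks (my assumed range), clearance falls at Week 17.5 to 22.5, so 5.5 to 10.5 weeks of Period 3.

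**Level over time.** Relative to the Week 12 trough, level = 0.5^((week − 12)/2), assuming one-compartment decline: 50% at Week 14, 25% at Week 16, 12.5% at Week 18, 6.3% at Week 20, 1.6% at Week 24. On the same model, exposure over Weeks 12 to 24 is about 19% of that over Weeks 0 to 12, and 95% of it falls before Week 20.

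**Receptor occupancy (illustrative).** Six doses reach 1 − 0.5^6 = 98% of steady state, so the 90% trough figure can be applied at Week 12. Assuming simple saturable binding, occupancy = c/(1 + c) with c = 9 × 0.5^((week − 12)/2): 82%, 69%, 53% and 36% at Weeks 14, 16, 18 and 20.

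**Who is in the placebo column.**

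| Grouping rule | Period 3 placebo column | Problem |
|---|---|---|
| As received (Protocol 9.3, SAP 5.3.1) | Sequence Group 1, about 45 | Residual LY3454738 to about Week 20 |
| As randomized (SAP 5.7) | Sequence Group 2, about 15 | Receiving LY3454738 |

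If Period 2 and Period 3 placebo were pooled as received, and everyone continued, 45/60 = 75% of placebo participants would be post-drug. Of the placebo person-weeks, (45 × 8)/(60 × 12) = 50% would precede clearance.

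**Size of the bias (assumed risks, not from the documents).** Take 12-week risks of 20% on drug and 5% on true placebo. Weekly hazards are −ln(0.80)/12 = 0.01860 and −ln(0.95)/12 = 0.00427, an excess of 0.01432.
- Full drug hazard to Week 20: 8 × 0.01860 + 4 × 0.00427 = 0.166. Risk = 1 − exp(−0.166) = 15.3%; difference 20 − 15.3 = 4.7 points.
- Excess proportional to occupancy: difference about 6 to 7 points.
- Excess proportional to drug level: the relative level integrates to 2.84 trough-weeks over Period 3. With the full excess set at the trough level, 12 × 0.00427 + 0.01432 × 2.84 = 0.092, risk 8.8%, difference 11.2 points. With it set at the steady-state average, which is 1.44 times trough, risk is 7.6% and the difference 12.4 points.
- No carry-over of effect: 15 points.

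**The case against.** The strongest objection is that the SAP never says the Period 3 placebo recipients are the comparator. The Fisher tests name no period, and under SAP 5.7 Sequence Group 1 stays in the LY3454738 column. This stands: a reader might infer that the Period 3 placebo group definitely serves as the control, or that Period 2 and Period 3 placebo are pooled, but no text states either. It does not remove the point, because the alternative rule places active treatment in the placebo column and nothing confines the tests to Period 2.

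Second, adverse events are counted by period, so Period 2 keeps a never-exposed control group. This stands in full. The primary and secondary efficacy analyses use Period 2, and Period 3 efficacy is summarized descriptively, so no efficacy result is touched.

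Third, 5 half-lives is a rule about detectability, not activity. This also stands. It would be too strong to say that the drug acts at full strength for 8 weeks: levels fall quickly, and acute infusion reactions would not be expected to carry over in this way. The 5-point figure is therefore near the worst case.

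Fourth, a reader might infer that laboratory change in Period 3 is definitely measured from an on-drug value. SAP 5.7 refers to 5.3.2, which gives Week 12, but 5.7.3 uses the baseline period. The text is unclear rather than clearly wrong.

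Finally, within Period 3 a by-sequence table gives the same planned counts as a by-treatment table. That is true; the gain is correct labels, no invalid p-value and no pooling.

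**Conclusion.** The point holds in a limited form. With no washout, Sequence Group 1 is expected to carry detectable LY3454738 for about 8 of the 12 Period 3 weeks (7 of 11 in the adverse-event window), with the level falling to about 6% of the Week 12 trough by Week 20. Neither grouping rule yields a valid Period 3 placebo comparator, and the Fisher tests and the laboratory and vital-sign ANCOVA are not restricted to Period 2.

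A Period 3 or pooled contrast may therefore be biased toward no difference. In the illustration, 15 points becomes about 5 to 12 if the effect persists, and stays at 15 if it does not. This rests on the protocol's approximate half-life, one-compartment decline and assumed event risks. The Period 2 safety comparison and all efficacy analyses are sound on this point. It is a cheap improvement, not a threat to the trial's main conclusions.

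**What to change.** 1. Reconcile SAP 5.3.1 (and Protocol 9.3) with SAP 5.7, so that one grouping rule applies to safety.
2. State in SAP 5.7, 5.7.2, 5.7.2.2, 5.7.3 and 5.7.4 that LY3454738-versus-placebo tests use Period 2 only.
3. Present Periods 3 and 4 descriptively by sequence (*LY3454738 then placebo*; *placebo then LY3454738*), without between-group tests. Do not pool Period 3 placebo with Period 2 placebo in any table, including the registry tables of SAP 5.11.
4. Say which laboratory baseline applies in Period 3 (SAP 5.3.2 or 5.7.3). For Sequence Group 1, also show change from the Week 0 value; SAP 5.3.2 already allows other baselines for supporting analyses.

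Reassigning Sequence Group 1 events up to Week 20 to LY3454738 is not needed once the display is by sequence. It would also require a person-time rule and a matching extension for Sequence Group 2 into Period 4.

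The cost is SAP wording and table shells; sample size and data collection do not change. The small downside is that Period 3 has no between-group p-value.

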5.3.2. Definition of Baseline and Postbaseline Measures

The baseline value for Period 2 is defined as the last nonmissing measurement on or before the date of first study drug administration (expected at Week 0). The baseline value for Period 3 is the last available value before the initial dose in Period 3 (expected at Week 12). Other definitions of the baseline value may be used to conduct additional supporting analyses.

A number of efficacy outcome measures are in the form of weekly scores derived from patient daily diary data. For these measures, the weekly score will be derived from the 7 days immediately prior to the study visit. The baseline score will be derived from the 7 days prior to Day 1 (Visit 2) for Period 2, and 7 days prior to Day 85 (Visit 9) for Period 3.

5.3.3. Patient Disposition

A detailed description of participant disposition will be provided, including a summary of the number and percentage of participants entered into the study, enrolled in the study, and treated,

as well as number and percentage of participants completing the study (participants who receive at least 1 dose of study drug and have at least 1 postbaseline assessment), or discontinuing (overall and by reason for discontinuation). A summary of all important protocol deviations will be provided.

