## 4.4. End-of-Study Definition

A participant is considered to have completed the study if he or she has completed all required phases of the study including the last visit or the last scheduled procedure shown in the SoA (Section 1.3).

The end of the study is defined as the date of the last visit or last scheduled procedure shown in the SoA (Section 1.3) for the last participant in the trial globally.

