#### Urticaria Patient Daily Diary (UPDD)

The UPDD is a daily diary completed twice per day (morning and evening) via an electronic, handheld device. Items asking about itch severity and number of hives pertain to the past 12 hours and are asked twice per day. The remaining items are asked once per day and pertain to the past 24 hours: interference with sleep, interference with daily activities, use of rescue medication (number of tablets), presence (and treatment) of angioedema, and any calls placed to healthcare professionals. While developed originally on paper, the electronic version of the UPDD has been shown to be equivalent to the paper version from a measurement perspective, and is considered a valid and reliable assessment of urticaria symptoms (Flood et al. 2013).

Pruritus, angioedema, and hives are monitored as clinical endpoints in the UPDD and would not constitute AEs. However, if any of these events is an SAE as defined in Appendix 10.3, Section 10.3.2, the event should be reported as an SAE. See Section 8.3.6 for more information.

There is no overall UPDD score calculation. The primary endpoint assessment (Urticaria Activity Score Over 7 Days [UAS7]) and key secondary endpoint assessments (Itch Severity Score Over 7 Days [ISS7] and Hives Severity Score Over 7 Days [HSS7]) are derived from data collected via the UPDD, as described below (Sections 8.1.1 and 8.1.2, respectively).

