# 9.4.1.1. Participant Disposition

A detailed description of participant disposition will be provided, including a summary of the number and percentage of participants entered into the study, enrolled in the study, and treated, as well as number and percentage of participants completing the study (participants who receive at least 1 dose of study drug and have at least 1 postbaseline assessment), or discontinuing (overall and by reason for discontinuation). A summary of all important protocol deviations will be provided.

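### The disposition rule counts a participant as completing the study after one dose and one postbaseline assessment, which contradicts protocol 4.4 and makes completers and discontinuations overlap

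*SAP*

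**What the plan says.** Two current definitions of the same term stand side by side.

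- **Disposition rule.** Protocol 9.4.1.1 will summarise "participants completing the study (participants who receive at least 1 dose of study drug and have at least 1 postbaseline assessment". SAP 5.3.3 repeats this, with the criterion "at least 1 dose of study drug and have at least 1 postbaseline assessment".
- **End-of-study definition.** Under protocol 4.4 a participant counts as complete only after having "completed all required phases of the study including the last visit or the last scheduled procedure shown in the SoA". Protocol 4.2 identifies the final visit as the "last post-treatment follow-up visit (Week 34, Visit 802".

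The disposition sentence goes on to the alternative outcome, "or discontinuing (overall and by reason for discontinuation". It lists participants entered, enrolled and treated, but does not say which of these is the denominator for the completion percentage.

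**The concern.** One dose plus one later assessment describes exposure, or at most evaluability. It does not describe completion, and it is met almost at once. Protocol 8.1 says that "The UPDD is a daily diary completed twice per day (morning and evening) via an electronic, handheld device". The Schedule of Activities (protocol 1.3) also places receptor occupancy samples up to 2 hours after the first infusion and a full visit at Week 1. Neither document says which assessment counts as the postbaseline one.

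A participant who withdraws just after the Week 1 visit therefore satisfies the completer rule and is also a discontinuation in the same table. The sentence joins the two categories with an *or*, as if they were alternatives, but they overlap. At stake is a reported descriptive result: a completion percentage that disagrees both with the protocol's own definition and with the discontinuation counts beside it.

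**Working it through.** **Inputs**

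- Planned counts: about 85 screened, 60 randomized, 52 evaluable (protocol 9.2, SAP 5.2).
- Study length after randomization: 34 weeks to Visit 802 (protocol 1.3, 4.2).
- First scheduled postbaseline visit: Visit 3, Week 1 (protocol 1.3).
- Assumed, because the documents give no figure: total dropout *d* among treated participants, and its timing.

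**The plan's own figures.** The documents state no expected completion rate, so there is none to reproduce. The nearest design figure is the power. Taking 52 evaluable as 39:13, a difference of 17 − 10 = 7 points, SD 7 and two-sided 0.05, power is 86.5% by the noncentral t and 87.7% by the normal approximation. This agrees with the protocol's figure of about 87%. The calculation does not use the completer definition.

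**Formulas, among treated participants.** Let *q* be the share of dropouts who leave before any postbaseline assessment.

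- Completion under protocol 4.4 = 1 − d
- Completion under the disposition rule = 1 − q·d
- Overstatement = (1 − q)·d, which is also the share counted in both categories

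**Illustration.** With a constant hazard over 34 weeks, the share lost by Week 1 is 1 − (1 − d)^(1/34), so the disposition rule reports (1 − d)^(1/34).

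| True dropout d | Complete, protocol 4.4 | Complete, disposition rule | Complete plus discontinued |
|---|---|---|---|
| 13.3% | 86.7% | 0.867^(1/34) = 99.6% | 112.9% |
| 30% | 70% | 0.70^(1/34) = 99.0% | 129.0% |
| 50% | 50% | 0.50^(1/34) = 98.0% | 148.0% |

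The 13.3% row is (60 − 52)/60 and treats all 8 non-evaluable participants as dropouts, which is an assumption. If the first assessment falls at Week 2 instead, the three reported figures are 99.2%, 97.9% and 96.0%.

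**Sensitivity to timing, at d = 30%** (protocol 4.4 gives 70%)

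| q | Disposition rule, 1 − 0.30q |
|---|---|
| 0 | 100% |
| 0.10 | 97% |
| 0.25 | 92.5% |
| 0.50 | 85% |
| 1 | 70% |

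The two definitions agree only if every dropout leaves before any assessment.

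**Denominator.** With about 85 entered participants as the base, reported completion could not exceed 60/85 = 71% under either definition.

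**The case against.** The strongest reply is that little depends on this row. The same sentence tabulates discontinuations overall and by reason, so attrition is visible. The mITT, per-protocol, safety and PK sets in SAP 5.3.1 do not use the completer definition, and neither does any test or estimate. All of that stands, and it limits the point to descriptive reporting.

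A reader might also draw three stronger conclusions, which the documents do not support.

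- **That reported completion will be near 100% whatever the true dropout.** This depends on when participants leave and on the denominator, and the plan fixes neither. With half of a 30% dropout occurring before any assessment, the figure is 85%. That timing is unlikely, because an assessment can come within hours or days of the first dose, but it is not excluded.
- **That 52 of 60 means 87% will have usable Week 12 data.** Evaluable is not defined in either document and is not tied to Week 12 scores or to dropout.
- **That the completion rate shows how much of the primary analysis rests on baseline carried forward.** Under SAP 5.4 and 5.5.1, imputation follows from a missing Week 12 UAS7, meaning fewer than 4 scored diary days in that week. A participant can miss that week and still finish the study, or provide it and leave in Period 3. The protocol 4.4 rate would be a poor measure of this too.

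Treating discontinuation simply as the complement of completion would also be wrong. Protocol 4.1 and 7.1 send participants who stop study drug early on to Visits 801 and 802, so stopping treatment and leaving the study are different events.

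**Conclusion.** The contradiction is real and lies in current text, both within the protocol (4.4 against 9.4.1.1) and between SAP 5.3.3 and protocol 4.4. Followed as written, the disposition rule overstates completion among treated participants by (1 − q)·d and counts those same participants twice. With a constant hazard and a first assessment at Week 1, both assumed, 13% to 50% dropout appears as 99.6% to 98% complete, and the two categories sum to about 113% to 148%. The gap narrows as more dropouts leave before any assessment.

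This is a minor point, but it concerns a wrongly stated rule and not merely a missing detail. It leaves the primary ANCOVA, the analysis populations and the power untouched, and it does not conceal dropout.

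**What to change.** 1. Remove the parenthetical definition from SAP 5.3.3 and define study completion by protocol 4.4. Align protocol 9.4.1.1, or record the change in the SAP and study report, which protocol 9.4 allows for changes that do not alter a principal feature.
2. State the denominator, for example treated participants by sequence group.
3. Report study completion and study discontinuation as mutually exclusive categories. Since the primary lock comes when Period 2 ends (SAP 5.9), show participants still in the study separately at that point. Say how someone who stops drug early but attends Visit 802 is classified.
4. Report separately, by sequence group, completion and discontinuation of study treatment in Period 2 (Week 12) and Period 3 (Week 24).
5. If the aim is to show reliance on BOCF, give the number of imputed Week 12 UAS7 scores by arm.
6. If the set with one dose and one later assessment is needed, give it another name.

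The cost is a small change to wording and table specifications, with no new data. The completion figure may look less favourable.
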